3. LIST OF ABBREVIATIONS

AE	adverse event
AESI	adverse event of special interest
ALT	alanine transaminase
AST	aspartate transaminase
AUC	area under the concentration-time curve
BUN	blood urea nitrogen
β-hCG	beta-human chorionic gonadotropin
CBC	complete blood count
CFR	Code of Federal Regulations
CHD	coronary heart disease
CKD	chronic kidney disease
CMP	comprehensive metabolic panel
CRA	clinical research associate
CRO	contract research organization
CVA	cerebrovascular accident
DNA	deoxyribonucleic acid
eCRF	electronic Case Report Form
ECG	Electrocardiogram
EDC	electronic data capture
EOS	End-of-Study (visit)
EOT	End-of-Treatment (visit)
ESRD	end-stage renal disease

FDA	Food and Drug Administration
FSI	first subject in
GCP	Good Clinical Practice
GLP	Good Laboratory Practice
HIPAA	Health Insurance Portability and Accountability Act
HIV	human immunodeficiency virus
ICF	informed consent form
ICH	International Conference on Harmonisation
ID	Identification
IEC	Independent Ethics Committee
IND	Investigational New Drug application
INR	International Normalized Ratio
IOM	Institute of Medicine
LSLV	last subject last visit
MedDRA	Medical Dictionary for Regulatory Activities
mRNA	messenger ribonucleic acid
NADP	nicotinamide adenine dinucleotide phosphate
NOAEL	no-observed-adverse-effect-level
PCR	polymerase chain reaction
PT	Pro thrombin Time
PTT	partial thromboplastin time
RBC	red blood cell
RNA	ribonucleic acid
SAE	serious adverse event
SD	standard deviation

14March2019

[figure not shown]
SMF	Site Master File
SOC	System Organ Class
SRC	Safety Review Committee
TIA	transient ischemic attack
U-VEGF121	Urinary Vascular Endothelial Growth Factors Isoform 121
Urinary VEGF-165	Urinary Vascular Endothelial Growth Factors Isoform 165
Urinary VEGF-189	Urinary Vascular Endothelial Growth Factors Isoform 189
Urinary VEGF-206	Urinary Vascular Endothelial Growth Factors Isoform 189
Urinary MCP-1	Monocyte chemoattractant protein 1,
Urinary Synaptopodin	Urinary Synaptopodin
Urinary TGF-beta	Urinary Transforming Growth Factor Beta
Urinary Podocalyxin	Urinary Podocalyxin
Urinary Nephryn	Urinary Nephryn
WBC	white blood cell
WHO	World Health Organization

Study Title	A Multicenter, Comparative Safety and Efficacy Study of ACTHar gel alone or in combination with oral Tacrolimus to reduce urinary proteinuria in patients with idiopathic DNA-JB9 Positive Fibrillary Glomerulopathy
Study Number	NN-002
Clinical Phase	Phase 4
Indication	Reduction of urinary protein excretion & slowing of GFR progression
Projected Number Enrolled Patients:	34
Projected Number NephroNet Sites:	7-10
Background	
Fibrillary glomerulonephritis (FGN) is a rare primary glomerular disease that is characterized by glomerular accumulations of nonbranching, randomly arranged fibrils. The most common histologic presentation is mesangial proliferative with areas of sclerosis. It is unknown whether specific histologic patterns have a better or worse prognosis. The deposition of fibrils can be found in the mesangium, basement membranes of glomerular endothelial cells and within the sub-epithelial space. Fibrillary proteins differ from amyloid both in diameter, arrangement and lack of Congo red staining. A recent review of all renal biopsies Arkana Laboratories between 2014-2015 demonstrated that 105 patients were diagnosed with Fibrillary GN (unpublished data). The mean age of these patients was 60 years old with a mean eGFR of 45 mls/min and UP/Cr ratio of 5.380 grams. The majority of these patients had been previously treated with 2 or more different immunosuppressive agents with little to no success.
 
There are currently no approved or generally accepted therapies for Fibrillary GN. Previous studies have shown that up to 70% of patients progress to ESRD within 4years⁹. Rituximab has been studied in two previous trials with an approximate response rate of 20%. A recent study treated 15 patients with refractory Fibrillary GN for an average of 6 months with ACTHar gel and achieved a complete or partial remission 59% of patients. Among the 7 ACTHar responsive patients, the UP/Cr ratio dropped by 75% from a mean of

Background

5435 to 1335 mg/gm. The efficacy of combination therapy with ACTHar and Tacrolimus was recently shown in a study of 22 patients with idiopathic Membranous GN (9) or FSGS (13). After 6 months of ACTHar gel therapy alone, 59% of patients achieved a complete or partial remission. When oral Tacrolimus was added to existing ACTHar gel, complete and partial response rates increased significantly to over 90%.

As shown in figure-1, the addition of tacrolimus to patients exhibiting a partial response to ACTH resulted in a further reduction in UP/Cr. While the number of patients in these

tri calcineurin inhibitor with a melanocortin receptor agonists could reduce proteinuria and stabilize renal function. The NephroNet clinical trial consortium is proposing a multicenter study investigating the safety and efficacy of ACTHar gel alone or combination with oral Tacrolimus in patients with Fibrillary glomerulopathy.

Study Design

This is a multicenter, Phase 4, prospective, open labeled study to compare the safety, tolerability, and efficacy of a 12-month course of ACTHar Gel alone or in combination with oral Tacrolimus to reduce UP/Cr ratio in patients with DNA-JB9 positive Fibrillary Glomerulopathy.

Hypothesis and Specific Aims	
Hypothesis#1: A 12-month treatment with combination ACTHar gel and Tacrolimus therapy will be superior to ACTHar gel therapy alone in lowering urinary protein to creatinine (UP/Cr) ratios in patients with idiopathic DNA-JB9 positive Fibrillary GN
 
Specific Aim #1-will randomize 35 patients with biopsy proven DNA-JB9 positive Fibrillary glomerulopathy to receive a 12-month course of ACTHar gel at 80 units SQ 2X/week alone or in combination with oral Tacrolimus at 1.0 mg BID (targeting for trough Tacrolimus dose of 4-6 ng/ml).
 
Hypothesis#2: Treatment with combination ACTHar gel and Tacrolimus therapy will result in a higher eGFR after 24 months of follow up than patients randomized to ACTHar gel therapy alone
 
Specific Aim #2-will determine the change in eGFR from baseline to 24 months of follow for patients with biopsy proven DNA-JB9 positive Fibrillary glomerulopathy. It is anticipated that at 24 months (12 months after completing therapy) patients randomized to ACTHar gel plus Tacrolimus will have higher eGFR compared to patients receiving ACTHar gel alone.
 
Hypothesis #3: Combination therapy of ACTHar Gel and Tacrolimus in patients with DNA-JB9 positive Fibrillary Glomerulopathy will lead to significantly lower urinary markers of podocyte injury compared to patients receiving ACTHar gel therapy alone.
 
Specific Aim #3-will compare the relative changes in the following urinary biomarkers will be performed:
 
1. Urinary VEGF 121, VEGF-1652. Urinary VEGF-189, VEGF-2063. Urinary MCP-14. Urinary Synaptopodin5. Urinary TGF-beta6. Urinary Podocalyxin7. Urinary Nephryn 
Levels will be measured at baseline prior to treatment and after 12 months of ACTHar ge therapyl alone or in combination with oral Tacrolimus. The relative reduction urinary biomarkers will also be compared between the two treatment groups.

Study Population	
A total of 34 patients will be enrolled.
 
Group 1 (17 patients) ACTHar gel 80 units 2X/week alone for 12 months of therapy.
 
Group 2 (17 patients) ACTHar gel 80 units 2X/week plus oral Tacrolimus 1.0 mg BID titrated to trough Tacrolimus levels between 4-6 ng/ml
 
Anticipated drop out rate 10%.

Inclusion Criteria	
Histologic Inclusion Criteria
 
Histologic Criteria: All patients with a diagnosis of The Fibrillary GN will be classified according to the Nasr nomenclature:
 
1) Renal biopsy demonstrating DNA-JB9 Positive staining within 3 years of study randomization2) Mesangial expansion with/without glomerular sclerosis3) Membranous changes with or without diffuse sclerosis4) Crescents or endocapillary proliferation5) Level of interstitial fibrosis 
Note: Patients with > 50% interstitial fibrosis will not be eligible for study participation
 
Note: Patients with monoclonal staining of fibrillary fibers will not be eligible for study participation
 
Inclusion Criteria:
 
1) Male/Female age \geq 182) Biopsy proven Fibrillary GN within 3 years of study randomization3) Stable Maximum RAAS inhibition X 4 weeks prior to randomization 
Note: Maximum RAAS inhibition will be left to the discretion of the site PI
 
4) eGFR > 25 mls/min calculate by the CKD-EPI formula5) UP/Cr ratio \geq 2000 mg/gm


Exclusion Criteria
	
5) Note: IF UP/Cr less than 2000 mg/gm, a formal 24-hour urine collection for total protein can be performed. The total 24-hour protein will need to >= 2000mg.
 
6) Blood pressure targeted to \leq 140/90 at the time of randomization
 
7) Patients with MGUS without history of myeloma WILL be eligible.
 
8) Patients with monoclonal staining for fibrillary fibers will be excluded
 
9) Patients with Type II non-insulin dependent diabetes WILL be eligible provided the renal biopsy does not show nodular Kimmelstiel Wilson lesions
 
Exclusion Criteria;
 
1) Patients with MGUS and history of myeloma WILL NOT be eligible
 
2) Patients with active viral production of either hepatitis B or C as evidence by historical PCR test positive for active viral shedding
 
3) HIV seropositivity
 
4) Renal biopsy data with > 50% Interstitial Fibrosis
 
5) Patient with active or a known history lymphoma
 
6) Patients with insulin Dependent diabetes mellitus will be excluded
 
Note: patients with Type II diabetes mellitus that are well controlled WITHOUT the need for insulin WILL be eligible for the study.
 
7) Patients with Type II non-insulin dependent diabetes WILL be eligible provided the renal biopsy does not show nodular Kimmelstiel Wilson lesions.
 
8) Patients receiving steroids, MMF, cyclophosphamide, Azathioprine or other immunosuppressive agent with 4 weeks of study randomization Note: Washout of these medications will be allowed at the screening visit
 
9) Patients having received Rituximab or B cell modifying biologic therapy within 6 months of randomization

----------------------------------	---

Primary Endpoint:	Primary Endpoint: The change in UP/Cr ratio in patients with biopsy proven Fibrillary GN after 12 months of treatment with treated with ACTHar gel (80 units SQ 2X/week) alone OR in combination with oral Tacrolimus (1.0 mg PO BID). The change in UP/Cr for each group will also be compared to baseline UP/Cr ratios prior to randomization
Secondary Endpoint	Secondary Endpoints: 
1) The relative change in UP/Cr at 24 months (12 months after stopping both ACTH and Tacrolimus) in the ACTHar gel group and the ACTHar gel + Tacrolimus group.2) The percentage of patients in the ACTHar gel alone versus ACTHar gel + Tacrolimus group that achieves complete, partial or clinical responses after 12 months of therapy3) The change in eGFR (measured by CKD-EPI formula) between the ACTHar gel and ACTHar Gel + Tacrolimus groups after 24 months of treatment with ACTHar gel alone or in combination with oral Tacrolimus. In addition, we will also compare the relative change in eGFR between those patients receiving ACTHar gel alone with those randomized to combination therapy.4) To compare the change in urinary biomarkers (see below) at baseline and after 12 months of treatment with ACTHar gel alone or in combination with Tacrolimus. The patients urinary biomarker levels after 12 months of therapy will be compared between the ACTHar gel alone group and ACTHar gel + Tacrolimus group.
a) Urinary VEGF 121, 165 189, and206b) Urinary MCP-1c) Urinary Synaptopodind) Urinary TGF-betae) Urinary Podocalyxinf) Urinary Nephryn 
Fibrillary GN patients with concurrent Type II diabetes mellitus: To determine whether ACTHar gel therapy resulted in


Number of total Clinic Visits
 
FACT-Trial: Study Design
	
conference call with the prospective patient will be arranged to discuss in details of the study; the risks/benefits of the study drug, as well as details regarding patient requirements and travel to and from the study site. The patient will be given time to review the consent with their families and other physicians.
 
If is determined by the Medical Director and the FACT Site PI that the patient is a likely candidate for the study, a travel agent will contact patient and make arrangements for airfare and overnight accommodations to visit the FACT PI. Both the airfare and overnight accommodations will be provided by NephroNet. If a patient lives within approximately 4 hours of the FACT site, they will be reimbursed for mileage and hotel. There will be a total of 13 visits per patient per site.
 
Patients agreeing to participate in the FACT sign consent at their first screening visit.
 
Thirteen (13) visits for total study: Pre-screening visits- two (2) Study Drug Treatment visits- six (6) Post Study Drug Treatment visits- five (5)
 
Study Design: This study will be a multi-center, prospective, randomized, open-labeled intervention trial of 34 patients randomized to 52 weeks of ACTHar gel alone or ACTHar gel plus oral Tacrolimus.
 
Drug Dosing:
 
Group-1: ACTHar gel alone-patients will be receive 80 units SQ Q 2X/week for 52 weeks
 
Group-2: ACTH gel 80 units 2X per week plus oral Tacrolimus (1.0 mg BID) titrating to a trough level of 4-6 ng/ml for 52 weeks
 
Note: Patient with type II diabetes will be allowed to dose at 24 units/day (0.3 mls SQ Q day) to reduce glucose fluctuations and simplify management of diabetes at the discretion of the PI.
 
Protocol-Schedule and Follow Up: Clinic Visits:

---	--

- **Visit 1: Pre-Randomization Screening & Consenting Visit:** Patients that have gone through the Pre-screening review and considered to be eligible for study participation will be seen by the local site PI for formal consenting two months prior to study randomization. The patient will then be seen by the FACT trial site PI who will perform a complete physical exam and obtain routine laboratory testing including a urine to protein Cr ratio.

Pre-Randomization Screening & Consenting Visit (V1): Blood and Urine Study Samples: Blood samples (5 mls) for serum and plasma will be obtained at each visit. Blood samples will be centrifuged at 3000 RPM for 5 minutes and 250 ul of plasma or serum will be transferred to an O-ring sealed cryovials and frozen at -80°C until analyzed. Each 10-ml sample of urine will be added to 100 ul of Thermo Scientific HALT proteinase inhibitor solution and then centrifuged at 3,000 rpm for 10 minutes at 4°C. Then, 250 µL of the urine supernatant will be transferred to an O-ring sealed cryovials and frozen at -80°C until analyzed.

- **Visit 2: Pre-Randomization Screening #2) "Optimization & Run-In Phase":** After the initial pre-screening visit, the prospective patients will enter a 4-week "optimization and run-in phase" during which patients will have their blood pressure optimized to a "pre-randomization" target level of 140/90. During the "run-in phase", RAAS blockers will not be modified and target blood pressure will be achieved using antihypertensive agents that do not alter urinary protein excretion (e.g. Nifedipine, Hydralazine).
- **Visit 3: Randomization/Baseline:** After the 4-week run-in phase, patient will be flown back to the FACT trial site where they will undergo formal randomization. When the site PI determines that the patient has met all inclusion and exclusion criteria, they contact [name] and the NephroNet data coordinating center for randomization. Each patient will then undergo a physical exam and routine blood and urine laboratory studies. The UP/Cr from the pre-

screening and randomization visits will be averaged and this value will be considered the “baseline UP/Cr” for that patient.

Note: If the pre-screen and randomization UP/Cr values differ by more than 50%, the patient will be allowed to collect a third UP/Cr ratio one week later. The average of those 3 UP/Cr ratios will be recorded as the patient’s baseline proteinuria.

Baseline- Blood and Urine Study Samples: Blood samples (5 mls) for serum and plasma will be obtained at each visit. Blood samples will be centrifuged at 3000 RPM for 5 minutes and 250 ul of plasma or serum will be transferred to an O-ring sealed cryovials and frozen at -80°C until analyzed. A 10-ml sample of urine will be centrifuged at 3,000 rpm for 10 minutes at 4°C. Then, 250 µL of the supernatant will be transferred to an O-ring sealed cryovials and frozen at -80°C until analyzed

- **Visit 4: 14 Days Post Randomization Visit:** 14 Days Post Randomization (Visit 4) will be optional for patients traveling from long distances. Would request that patient visit nephrologist in home town if any adverse events of concern are reported.
- **Visits 5 – 7: Study Visits-Months 3 (V5), 6(V6) & 9(V7) :** We will be conducted in like manner to Randomization visit. Each patient will get a complete physical exam. Standard blood and urine studies will be performed as well as plasma, serum and urine study sample collections. Tacrolimus Trough Levels will be drawn for those patients randomized to the Tacrolimus arm.
- **Visit 8: Month 12: Primary Endpoint Evaluation:** All patients completing of 52 weeks of ACTHar gel therapy alone or in combination with Tacrolimus will be examined for their change in UP/Cr as compared to their baseline levels of urinary protein. Patients will be asked to bring 2 first morning voids of urine. These two samples will be averaged and used for

determination of the percentage of patients achieving the primary endpoint.

Complete Responders: < 300 mg/gm UP/Cr ratio

Patients that have reached this milestone will be weaned off ACTHar Gel with or without Tacrolimus over the subsequent 14 days.

Sites will start the ACTHar Gel wean at 40 units and reduce over a 2 week taper period at the discretion of the principal investigator of each site.

Non-or Partial Responders: > 50% Reduction in UP/Cr ratio to minimum value of 2000 mg/gm:

Patients will follow the same weaning protocol as the complete responders described above.

- **Visit 9: ACTHar Washout Visit:**

14 Days Post End of Treatment (Visit 9) will be optional for patients traveling from long distances and will occur after the post treatment taper. The Study Staff will request that the patient visit a Nephrologist in the patient's home town if any adverse events of concern are reported.

- **Visits 10 -12: Follow-Up Visits-Months 15 (V10), 18(V11) & 9(V12):** We will be conducted in like manner to Randomization visit. Each patient will be get a complete physical exam. Standard blood and urine studies will be performed as well as plasma, serum and urine study sample collections.

- **Visit 13: Month 24 Visit: Secondary Endpoint Evaluation:**

Patients completing 104 weeks of study participation will be evaluated for the following:

1) Percentage of Complete Responder patients weaned off ACTHar gel and Tacrolimus that developed a relapse after 12 months of no therapy.

2) Percentage of patients in the ACTHar gel alone group that demonstrated additional reduction in UP/Cr

ratio following the addition of Tacrolimus at Week 52.

Hyperkalemia: Patient developing hyperkalemia defined as > 5.5 meq/L will undergo the following interventions:

Intervention #1: Review dietary sources of potassium and assess patient compliance with prescribed dietary restrictions.

Intervention #2: Adding or increasing dose of a loop diuretic. If they patient was already taking a diuretic as part of their standard of care regimen, the dose or frequency will be increased according to the discretion of the Site PI.

Intervention #3: For patients with continued hyperkalemia following intervention 1 & 2, the Site PI can consider adding a Thiazide diuretic (HCTZ or Metolazone) to the current loop diuretic.

Intervention #4: For patients with continued hyperkalemia following intervention 1 & 2 & 3, the dose of Tacrolimus can be reduced to 0.5 mg BID.

Combining Thiazide and Loop diuretic therapy to AM-PM doses

Intervention #5: For patients with continued hyperkalemia following intervention 1 & 2, 3, & 4, the patient can discontinued from Tacrolimus.

Note: Any Site PI that chooses to treat a study patient's hyperkalemia with Patiromer may do and keep the patient in the study. Any decision to use Patiromer is solely at the discretion of the Site PI.

Hyperglycemia: Patients developing intractable hyperglycemia defined as > 400 mg/dl can have their current diabetic medications modified. For patients with continued hyperglycemia despite increases in diabetic therapy, the dose of ACTHar gel can be reduced by 50%. Patients with persistent hyperglycemia can be withdrawn from the study at the discretion of the Site PI.

Note: Any Site PI choosing to use of Insulin to treat a study patient's hyperglycemia can do and keep the patient in the

study. Any decision to use institute Insulin therapy is solely at the discretion of the Site PI.

Lower Extremity Edema: Patients developing increasing lower extremity edema can have their diuretic regimen increased by either dose or frequency. Patients continuing to have edema with maximal Loop diuretics can be treated with dual Loop and Thiazide diuretic therapy. All decisions as the management of lower extremity edema will be left to the discretion of the Site PI.

Statistical Analysis Sample Size and Power.

The sample size was calculated to detect a 40% difference in the mean UP/Cr ratio after 12 -month of ACTHar gel therapy alone or with oral Tacrolimus. Analysis will be intention to treat for all patient receiving at least one week of drug therapy. Based on the estimated variability of 30% for the change in UP/Cr ratio (CV) a sample size of 17 patients per arm (total-34) will be needed to provide 80% power to see a difference with a P value of < 0.05. A Fisher exact test will be applied for comparisons of adverse event frequencies. All tests were two-tailed with a P value-0.05 considered significant.

References:

- 1) Laser Microdissection and Proteomic Analysis of Amyloidosis, Cryoglobulinemic GN, Fibrillary GN, and Immunotactoid Glomerulopathy Sanjeev Sethi,* Jason D. Theis,* Julie A. Vrana,* Fernando C. Fervenza,† Anjali Sethi,‡ Qi Qian,† Patrick Quint,* Nelson Leung,* Ahmet Dogan,* and Samih H. Nasr* *Clin J Am Soc Nephrol* 8: 915–921, 2013.
- 2) Fibrillary Glomerulonephritis: A Report of 66 Cases from a Single Institution *Samih H. Nasr,* Anthony M. Valeri,† Lynn D. Cornell,* Mary E. Fidler,* Sanjeev Sethi,* Nelson Leung,‡ and Fernando C. Fervenza‡ Clin J Am Soc Nephrol* 6: 775–784, 2011.
- 3) Fibrillary Glomerulonephritis and Immunotactoid Glomerulopathy Charles E. Alpers and Jolanta Kowalewska. *J Am Soc Nephrol* 19: 34–37, 2008.
- 4) Plasmapheresis leading to remission of refractory

14March2019

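### Women are eligible from age 18, but no exclusion criterion covers pregnancy and no visit includes a pregnancy test.

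*Protocol*

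**What the plan says.** Inclusion Criteria, item 1 ("Male/Female age") admits both sexes from 18 years with no upper limit. Item 3 requires "Stable Maximum RAAS inhibition X 4 weeks prior to randomization", with the meaning of maximum left to the site investigator. During the run-in at Visit 2, "RAAS blockers will not be modified". The schedule then marks stable ACE inhibitor or ARB use at every visit from Visit 1 to Visit 13, which is month 24.

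Under Drug Dosing, Group 1 is described as "ACTHar gel alone-patients will be receive 80 units SQ Q 2X/week for 52 weeks". Group 2 adds oral tacrolimus, "titrating to a trough level of 4-6 ng/ml for 52 weeks". Visit 8 adds a taper of about two weeks.

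The Exclusion Criteria have nine numbered items: myeloma, hepatitis B or C, HIV, interstitial fibrosis, lymphoma, insulin-dependent diabetes, diabetic lesions on biopsy, recent immunosuppression, and recent rituximab or other B-cell therapy. Pregnancy, breastfeeding and contraception are not mentioned. The only trace of a pregnancy test is in the List of Abbreviations, where β-hCG is spelled out as "beta-human chorionic gonadotropin".

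**The concern.** Eligibility rules and visit procedures are what sites act on, and they belong in the protocol, so a separate analysis plan would not supply them. If the rule is followed to the letter, pregnancy does not stop randomisation and nothing in the schedule is designed to detect it. The first stake is the safety of the woman and the pregnancy under study drug and RAAS inhibition.

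The second stake is the data. Pregnancy can itself change protein excretion and GFR, which are the quantities behind the primary endpoint and the eGFR endpoint. It also calls into question the RAAS stability that the plan relies on when it compares UP/Cr over time.

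**Working it through.** No sample-size or power figure is involved, so the check is to set the relevant parts of the protocol side by side.

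1. **Who may enter.** Any man or woman aged 18 or over who meets the renal, blood pressure and RAAS conditions. No condition refers to childbearing potential.
2. **Who is kept out.** The nine exclusions run without a break into the Primary Endpoint section, and no item concerns pregnancy.
3. **What is tested.** Before randomisation (Visits 1 to 3) the schedule lists CBC, CMP, UA, UP/Cr and urinary biomarkers. HgbA1c and tacrolimus trough levels come later. No row and no visit description names a pregnancy test. In the whole supplied text, pregnancy, lactation or contraception is mentioned 0 times, and β-hCG once.
4. **What triggers randomisation.** At Visit 3 the site investigator contacts the coordinating centre once the inclusion and exclusion criteria are judged met. The text places that visit's examination and laboratory work after this step, so nothing in the Visit 3 laboratory work informs allocation.
5. **How long the exposure lasts.** Study drug runs 52 weeks plus the taper, and total participation is 104 weeks. Since 104 − 52 = 52, month 24 is about a year after treatment, which agrees with the first secondary endpoint ("12 months after stopping both ACTH and Tacrolimus"). The third secondary endpoint reads differently: "after 24 months of treatment with ACTHar gel alone or in combination with oral Tacrolimus". These statements conflict and must be reconciled. The dosing text, the visit plan and the first secondary endpoint all point to 12 months. The ACE inhibitor or ARB row does run to month 24, but the word maximum is attached only to the four weeks before randomisation.
6. **Which data are exposed.** Baseline UP/Cr is the mean of the pre-screening and randomisation values, with a third value allowed if the two differ by more than 50%. In a woman already pregnant at entry, one or more of these values could be taken during pregnancy, as could the early on-treatment values. By month 12 that pregnancy would normally have ended. The main route to the primary endpoint is therefore the baseline from which change is measured.
7. **What one patient weighs.** With 17 per arm, one patient is 1/17 = 5.9% of an arm. The anticipated 10% dropout is 0.10 × 17 = 1.7 patients per arm. Both figures apply to a patient lost for any reason. They describe how small the trial is and say nothing about how often pregnancy would occur.

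**The case against.** The strongest case on the other side is that this is an omission in a rare situation that ordinary care would catch. The Background cites a mean age of 60 in a biopsy series. Candidates have their records reviewed by the national and local investigators, must already be on stable RAAS inhibition, and have a full history and examination at Visit 1. Consent pages are not in the supplied text, which also breaks off between the Secondary Endpoint section and the section on the number of clinic visits, so pregnancy wording could sit there. Much of this stands as a reason to expect few cases. It does not close the gap: clinical alertness is not a criterion, and the exclusion list and laboratory schedule both look complete without the item.

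Four stronger readings are tempting, and the document does not support them.

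- A reader might infer 24 months on study drug. Treatment is 52 weeks plus a taper; only the ACE inhibitor or ARB row extends to month 24.
- A reader might take the β-hCG abbreviation as a planned test that was then dropped, and so as an internal contradiction. Many other entries in that list (NOAEL, NADP, IOM, INR, TIA and AUC among them) are also unused, so it looks like template text and is supporting evidence at most.
- A reader might assume that 10–20% of the 34 patients are women under 45, which gives 3.4 to 6.8, and call them affected. The protocol gives no sex split, no age distribution and no pregnancy rate, and being of childbearing age is not the same as being pregnant.
- A reader might argue that the month-12 and month-24 values themselves would be spoiled. Pregnancies that coincide with those visits would mostly begin after randomisation, and entry testing does not prevent them.

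**Conclusion.** The point holds as a gap in the eligibility rule: as written, pregnancy is neither excluded nor looked for before allocation. Its weight is mainly patient safety. The statistical consequence is secondary and limited to possible distortion of an affected patient's baseline and early UP/Cr and eGFR.

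Frequency cannot be estimated from the document and is probably low. That judgement rests on the cited mean age, which comes from a biopsy series and not from the trial's own patients. The conclusion also assumes that the criteria and schedule as supplied are complete, which their numbering and layout suggest. It should be corrected because the consequence could be serious and the correction is cheap.

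**What to change.** Add pregnancy to the Exclusion Criteria. Add a β-hCG row to the schedule for women of childbearing potential at Visit 1 and Visit 3, run on blood or urine already collected at those visits.

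Visit 1 alone is not enough, because it falls two months before randomisation. At Visit 3 the result has to be available before the coordinating centre is contacted, so the visit description should place the test ahead of allocation.

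The cost is one exclusion line, one schedule row, and an inexpensive assay at two visits that already include sampling. No visit is added. How a pregnancy that arises during the trial is managed is for the sponsor and investigators to decide.

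### Exclusion 2 rests on an undated historical positive hepatitis B or C PCR, and no visible step requires any hepatitis result before randomisation

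*Protocol*

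**What the plan says.** Exclusion Criteria, item 2, removes "Patients with active viral production of either hepatitis B or C as evidence by historical PCR test positive for active viral shedding". It gives no look-back period and does not say what to do when the file holds no result.

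The visible steps before randomisation are these:

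- **Pre-screen.** Footnote 1 of the schedule of assessments has the national and local investigators check existing records for eligibility. Visit 1 then takes "Patients that have gone through the Pre-screening review and considered to be eligible for study participation".
- **Visit 1**, planned two months before randomisation. The site investigator is to examine the patient and "obtain routine laboratory testing including a urine to protein Cr ratio". Study samples are also taken: "Blood samples (5 mls) for serum and plasma will be obtained at each visit".
- **Visit 2.** A 4-week run-in to bring blood pressure to target.
- **Visit 3.** Routine blood and urine studies. The site investigator decides that all criteria are met, and the patient is randomised.

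The schedule lists no hepatitis B or C test at any visit.

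Other criteria that depend on the patient's history do carry dates. Inclusion 2 requires "Biopsy proven Fibrillary GN within 3 years of study randomization". Exclusion 9 bars "Patients having received Rituximab or B cell modifying biologic therapy within 6 months of randomization". Exclusion 8 covers steroids, named agents or "other immunosuppressive agent with 4 weeks of study randomization", and allows washout at screening.

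**The concern.** An exclusion for active infection protects patients only if someone finds out whether the infection is present. This rule points the site to old records and is silent when those records are empty or out of date. The infection that nobody has looked for is the one it lets through.

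The stake is patient safety. By writing the exclusion, the protocol itself treats active hepatitis B or C as a reason not to give this treatment. Treatment lasts 52 weeks, and half the patients also receive tacrolimus titrated to a trough level. Previous immunosuppression may be common in this disease. Of the pathology series in the Background, the protocol says: "The majority of these patients had been previously treated with 2 or more different immunosuppressive agents with little to no success". A hepatitis result on file could predate such treatment. That series reports nothing about hepatitis testing, so this is a possibility and not a measured rate.

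**Working it through.** No formula applies, and the protocol gives no figure to reproduce. The check is to follow the rule, as worded, for each type of patient.

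**Step 1: what the rule needs in order to exclude.** It needs active viral production, shown by a past PCR that was positive.

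**Step 2: apply it to four patients, all infected at randomisation except the last.**

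| Patient | Positive PCR on file? | Caught by the wording? |
|---|---|---|
| Infected, with a past positive PCR | Yes | Yes |
| Infected, never tested | No | No |
| Infected after a past negative test | No | No |
| Not infected, never tested | No | No (correctly eligible) |

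On paper, the second and third patients cannot be told apart from an uninfected patient.

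**Step 3: does another visible step separate them?**

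- The record review can find only tests already done.
- The laboratory work at Visits 1 and 3 is described as routine, and no viral test is named.
- A metabolic panel is drawn at Visits 1, 2 and 3. An abnormal result might prompt a hepatitis test, but no visible rule links the two.
- The investigator's eligibility decision at Visit 3 applies the criteria as written and adds no required result.

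**Step 4: compare with the other dated criteria.** Inclusion 2 cannot be met without a biopsy record from the last 3 years, so an empty file fails. Exclusion 9 fixes a 6-month look-back. Exclusion 2 has neither feature: an empty file passes, and a result of any age counts.

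**Step 5: number exposed.** The Study Population section gives 17 + 17 = 34 patients, 17 of them assigned to tacrolimus. The protocol gives no hepatitis prevalence and no share of patients already tested, so no expected number of missed cases can be calculated.

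**The case against.** **Part of the pre-screening text is not available.** The description resumes mid-sentence, and the lost part may ask for a recent hepatitis result. If it does, the safety point falls away. This objection stands as a condition on the finding. What is visible makes a study-ordered test at that step unlikely: consent is signed at the first screening visit, and the schedule marks only the privacy release at pre-screen. A request for a recent outside result remains possible.

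**The condition excluded is active infection, and the PCR clause only names the evidence.** This is a fair reading. An investigator who knew of a current infection would presumably exclude the patient, and nothing forbids ordering a test. The gap is therefore confined to infections that nobody knows about. The same reading answers a further inference, that an old positive PCR would wrongly bar a patient who has since cleared the virus. Such a patient has no active viral production, so that harm is not claimed here.

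**The schedule also shows no test for HIV, myeloma or lymphoma.** This is correct. The table evidently does not list every eligibility check, so the absence of a hepatitis row proves little by itself. The point rests on the wording of exclusion 2, which makes a historical result the evidence without requiring that one exist.

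**The age of results on file is unknown.** A reader might take the 3-year biopsy window as a limit on how old a hepatitis result could be. The protocol does not tie hepatitis testing to the biopsy, so no such limit can be inferred.

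**Conclusion.** The point holds as a safety weakness in a stated eligibility rule. As worded, exclusion 2 does not catch a patient who was never tested for hepatitis B or C or who was infected after the last test, and no visible step before randomisation closes that gap. It should be changed because the remedy is cheap and the protocol already regards active infection as a bar to treatment.

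Its size is limited. At most 34 patients are exposed, and the number with an undetected infection cannot be estimated from the document. A reader might infer that infected patients will be enrolled or that sites will not test. The protocol supports neither; it shows only that testing is not required in the visible text. A reader might also look for an effect on the trial's result. There is none to claim: the primary comparison of UP/Cr and the power are untouched.

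Confidence is medium. The finding assumes that the missing part of the pre-screening description does not require a recent hepatitis result.

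**What to change.** First check the full pre-screening text. If it does not already require a recent hepatitis result:

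1. Reword exclusion 2 to current active hepatitis B or C infection and remove the reliance on a historical PCR.
2. Require a hepatitis B and C result before randomisation, by one of two routes:
   - serology at Visit 1 with reflex PCR if positive, where viraemia on PCR excludes the patient and a serology-positive, PCR-negative patient is not excluded by this item; or
   - a documented result within a stated window before randomisation, for example 6 months, which matches the look-back in exclusion 9.
3. Add the test to the schedule at Visit 1.

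**Cost.** A few assays per screened patient. Blood is already drawn at Visit 1, and two months remain for the result to come back. The protocol gives no screen-failure rate. Over an assumed range of 0% to 30%, the number of panels runs from 34/(1 − 0) = 34 to 34/(1 − 0.30) = 48.6, about 49, and fewer if recent outside results are accepted. There may be an occasional extra screen failure, and a short amendment is needed. The sample size and the analysis do not change.
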